#### 5.1.4 Study treatment preparation and administration

Detailed information about the study treatment preparation and stability of the solutions is provided within the study treatment handling manual.

The preparation of the study treatment must be done under aseptic conditions by a pharmacist or an authorized person according to local regulation.

The sealed glass vials containing ACT-246475 will be reconstituted with 1 mL of water for injection. The resulting stock solutions will be at a concentration of 20 mg/mL ACT-246475. For subjects randomized to receive the 8 mg dose of ACT-246475, an additional dilution of the stock solution will be performed with 1 mL of NaCl 0.9% to obtain the required concentration for injection [Table 1].

The reconstituted ACT-246475 solution will be injected as a s.c. single dose in the anterior mid-thigh skin through [REDACTED] needle. The injected volume will be 0.8 mL for all subjects [REDACTED]

The protocol-mandated study treatment administration procedures may not be altered without prior written approval from sponsor. An accurate record of the date and amount of study treatment administered to each subject must be available for inspection at any time.

[REDACTED]

In Table 1, the preparation of doses of the study treatment is described; detailed instructions are given in the study treatment handling manual.

The date and start time of preparation of the injection solution as well as the procedure must be recorded on source documents.

**Table 1** Preparation of study treatment for s.c. administration

Study treatment	Dose	Volume of water for injection	Volume of NaCl 0.9%	Stock solution concentration	Aliquot of stock solution to be administered
ACT-246475	8 mg	1 mL	1 mL	10 mg/mL	0.8 mL
ACT-246475	16 mg	1 mL	Not applicable	20 mg/mL	0.8 mL

### 5.1.5 Blinding

Not applicable.

### 5.1.6 Unblinding

Not applicable.

### 5.1.7 Study treatment accountability and compliance with study treatment

#### 5.1.7.1 Study treatment accountability

The inventory of study treatment dispensed and returned (i.e., study-treatment accountability) must be performed by site personnel. It is to be recorded by site personnel on the study-treatment dispensing and accountability log and in the electronic case report form (eCRF), verified and reconciled by the CRA during the routine site visits and at the end of the study. The study treatment accountability in the eCRF will include at least the following information for each study treatment unit (i.e., vial) administered to the subject:

- Dispensed vial number
- Date vial dispensed

All study treatment supplies, including partially used or empty vials, must be retained at the site for review and reconciliation by the CRA.

#### 5.1.7.2 Study treatment compliance

Study treatment compliance is based on administration of the study treatment as allocated. Any deviation from randomization allocation will be reported as a protocol deviation.

### 5.1.8 Study treatment dose adjustments and interruptions

Study treatment dose adjustments are not permitted.

Study treatment interruptions are not applicable for this single dose study.

### 5.1.9 Premature discontinuation of study treatment

Not applicable (single-dose study).

### **5.1.10 Study-specific criteria for interruption / premature discontinuation of study treatment**

Not applicable (single-dose study).

## **5.2 Previous and concomitant therapy**

### **5.2.1 Definitions**

A previous therapy is any treatment for which the end date is prior to giving informed consent.

A therapy that is study-concomitant is any treatment that is ongoing or initiated after providing informed consent, or initiated up to EOS.

A therapy that is study treatment-concomitant is any treatment that is either ongoing at the start of study treatment or is initiated up to 48 hours after study treatment administration.

### **5.2.2 Reporting of previous/concomitant therapy**

The use of all study-concomitant therapy (including traditional and alternative medicines, e.g., plant-, animal-, or mineral-based medicines) will be recorded in the eCRF.

Previous therapies related to treatment and prevention of CAD will be recorded in the eCRF if discontinued less than 1 month ( $\leq 30$  days) prior to providing informed consent. Previous therapies related to treatment of the study-qualifying AMI will be recorded in the eCRF.

The generic name, start/end dates of administration (as well as whether it was ongoing at administration of study treatment and/or EOS), route, dose, and indication will be recorded in the eCRF. In addition, for oral P2Y12 receptor antagonists, the time of each administration during the study will be recorded in the eCRF.

### **5.2.3 Allowed concomitant therapy**

Standard treatment of AMI is allowed including anticoagulants and oral P2Y12 receptor antagonists.

When initiation of an oral P2Y12 receptor antagonist is considered for a subject [see also Section 1.4.2], it must be initiated after administration of ACT-246475. In absence of clinical data regarding administration of an irreversible P2Y12 antagonist following the administration of ACT-246475, it is requested to use a reversible oral P2Y12 receptor antagonist (e.g., ticagrelor).

## 5.2.4 Forbidden concomitant therapy

The following medications are prohibited from screening and up to the last PK blood collection:

- Fibrinolytic therapy (e.g., streptokinase, alteplase...).
- OATP1B1 and OATP1B3 inhibitors (e.g., atazanavir, ritonavir, lopinavir, simeprevir, clarithromycin, erythromycin, cyclosporine, eltrombopag, lapatinib, gemfibrozil, rifampin)
- Glycoprotein IIb/IIIa inhibitors.
- Irreversible oral P2Y12 antagonists (clopidogrel or prasugrel)
- Cangrelor

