	
and oral P2Y12 receptor antagonists.
 
When initiation of an oral P2Y12 receptor antagonist is considered for a subject, it must be initiated after administration of ACT-246475. In absence of clinical data regarding administration of an irreversible P2Y12 antagonist following the administration of ACT-246475, it is requested to use a reversible oral P2Y12 receptor antagonist (e.g., ticagrelor).
 
Forbidden concomitant therapy
 
The following medications are prohibited from screening and up to the last PK blood collection:
 

• Fibrinolytic therapy (e.g., streptokinase, alteplase...).

• OATP1B1 and OATP1B3 inhibitors (e.g., atazanavir, ritonavir, lopinavir, simeprevir, clarithromycin, erythromycin, cyclosporine, eltrombopag, lapatinib, gemfibrozil, rifampin).

• Glycoprotein IIb/IIIa inhibitors.

• Oral irreversible P2Y12 antagonists (clopidogrel or prasugrel).

• Cangrelor.

ENDPOINTS	
Primary endpoint
 
The primary endpoint is the response to the treatment defined for each subject as a P2Y12 reaction units value < 100 at the 30 min post-dose time point, as measured via VerifyNow®. This corresponds to an IPA induced by ADP > 80%.
 
Safety endpoints
 
The safety endpoints will be assessed up to EOS, i.e., over 48 hours post treatment administration:
 

• Treatment-emergent adverse events (AEs) and serious adverse events.

• AE of specific interest (AESI): Hemorrhage.

• Change in vital signs (systolic and diastolic arterial blood pressure and pulse rate) from baseline to all assessed time

 A treatment-emergent AE is any AE temporally associated with the administration of study treatment (until 48 hours after study treatment administration) whether or not considered by the investigator as related to study treatment.

	
points during the study.
 

• Change from baseline for clinical laboratory tests.

• Treatment-emergent marked laboratory abnormalities.

 
Pharmacokinetic endpoints
 
PK endpoints include maximum plasma concentration (<math>C_{max}</math>) and time to reach <math>C_{max}</math> (<math>t_{max}</math>).

ASSESSMENTS	Refer to the schedule of assessments in Table 2 .

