#### **1.4.2 Interference with oral P2Y12 receptor antagonists**

Co-administration of the oral, irreversible P2Y12 receptor antagonists clopidogrel and prasugrel during infusion of cangrelor is prohibited given the potential lack of clopidogrel- / prasugrel-mediated IPA [Kengrexal® SmPC]. Mechanistically, this is due to the short half-life of the active metabolites of clopidogrel and prasugrel that, while still in the circulation, cannot bind to the receptor which is pre-occupied by cangrelor. Instead, if administered immediately after stopping the cangrelor infusion, clopidogrel and prasugrel both exhibit their expected PD effects [Steinhubl 2008, Schneider 2014, Judge 2016, Rollimi 2016].

*In vitro* studies have been conducted to assess the PD interaction potential of ACT-246475 with ticagrelor and the active metabolite of prasugrel (P-AM) [B-16.064]. Here, additive effects were determined when ACT-246475 was added to platelets pre-bound to ticagrelor or P-AM. Instead, if P-AM was added to platelets pre-bound to ACT-246475 the inhibitory effects of P-AM on platelet aggregation were reduced.

Because of the current ESC guidelines [Valgimigli 2018] recommending administration of a loading dose of oral P2Y12 receptor antagonist as early as possible after diagnosis of an AMI, it is expected that many subjects participating in the study will receive an oral P2Y12 antagonist.

In the absence of clinical data regarding administration of the irreversible P2Y12 antagonists clopidogrel or prasugrel following administration of ACT-246475, if oral treatment with a P2Y12 receptor antagonist is to be initiated in subjects participating in this study, a reversible P2Y12 receptor antagonist (e.g., ticagrelor) must be used.

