### 3.1.2 Study duration

The study starts with the first act of recruitment (i.e., informed consent provided by the first subject) and ends with the completion of the last subject's EOS assessments.

The overall duration of participation in the study (including screening period) of a subject will be approximately 2 days.

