**Table 2 Visit and assessment schedule**

PERIOD	SCREENING	TREATMENT PERIOD					
Visit	Visit 1						
Time point	Pre-dose	0 min	15 min ±5 min	30 min ±5 min	60 min ±5 min	8 h / Post- procedure 	EOS 48 h ±2 h
Informed consent	X						
Eligibility	X						
Demographics and Medical history (including TIMI risk score and Killip class of MI)	X						
Physical examination	X						
Body weight and height (estimated)	X						
Previous/concomitant therapy	X		X				X
Vital signs (BP and PR)	X			X	X		X
PK blood sampling			X	X	X	X 	
VerifyNow®	X		X	X	X		
Laboratory tests	X						X
hsTnT	X						
s.c. injection of ACT-246475		X					
AEs/SAEs	X		X				X

(S)AE: (serious) adverse event; BP: blood pressure; EOS: End-of-Study; hsTnT: high sensitivity troponin T; MI: myocardial infarction; PCI: percutaneous coronary intervention; PK: pharmacokinetic; PR: pulse rate; s.c.: subcutaneous; TIMI: thrombolysis in myocardial infarction.

- The 8 h PK post-dose time point is flexible. If the subject gets an invasive procedure (PCI/angiography) within 8 h of study drug administration, the blood sample is to be collected at the end of the procedure. If no invasive procedure is performed within 8 h of study drug administration, the blood sample is to be collected approximately 8 h after study drug administration.

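### The clopidogrel/prasugrel ban in Protocol 5.2.4 ends at a movable PK sample, and 5.2.3 only requests what 1.4.2 makes mandatory; set one rule and one fixed post-dose end time

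*Protocol*

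**What the plan says.** The choice of oral P2Y12 antagonist after ACT-246475 is governed in several places in the Protocol.

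- **Section 1.4.2.** If oral treatment "is to be initiated in subjects participating in this study", a reversible "receptor antagonist (e.g., ticagrelor) must be used". No end time is given. The reason stated is the lack of clinical data on an irreversible agent given after ACT-246475. The section also reports an in vitro result: when the active metabolite of prasugrel (P-AM) was added to platelets already carrying ACT-246475, "the inhibitory effects of P-AM on platelet aggregation were reduced". Section 3.1.2 says that participation "of a subject will be approximately 2 days".
- **Section 5.2.3 and the synopsis.** Here "it is requested to use a reversible oral" agent. In 5.2.3 the words "is considered for a subject [see also Section 1.4.2" point back to the mandatory text. The synopsis has no such pointer.
- **Section 5.2.4 and the synopsis.** Clopidogrel and prasugrel are among the drugs "prohibited from screening and up to the last PK blood collection".
- **Table 2, footnote 1.** The nominal 8 h PK sample is flexible. If PCI or angiography takes place within 8 h, "the blood sample is to be collected at the end of the procedure"; otherwise it is taken at about 8 h.

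SAP Appendix A reproduces the synopsis wording.

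**The concern.** The reason for avoiding clopidogrel and prasugrel is receptor occupancy. Their active metabolites are short-lived and may find the receptor already taken. The end of the ban, however, is set by a blood-sampling event that has no link to occupancy. The earlier the procedure ends, the sooner the ban in 5.2.4 lifts and the more ACT-246475 is likely to be present. A subject with no procedure is covered to about 8 h; a subject with early PCI is covered for less.

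All subjects are scheduled for an invasive strategy (3.1), so the procedure branch of the footnote is not exceptional. A site working only from 5.2.3, 5.2.4 or the synopsis could start an irreversible agent straight after an early procedure and believe it was compliant. At stake is possible under-inhibition of platelets in a patient with acute MI once ACT-246475 wears off. Recording each oral P2Y12 dose time (5.2.2) and the sponsor and ISEC safety reviews could detect such a case but would not prevent it.

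**Working it through.** **1. Strength and duration of each rule**

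| Place | Strength | Ends |
|---|---|---|
| 1.4.2 | Mandatory | Not stated |
| 5.2.3, synopsis (allowed therapy) | Request | Not stated |
| 5.2.4, synopsis (forbidden therapy) | Ban | Last PK sample |

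Until the last PK sample the ban is firm. From that sample to the end of the study, only 1.4.2 is mandatory.

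**2. Earliest possible end of the ban under 5.2.4**

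The last PK sample is the later of the 60 min sample (window ±5 min, Table 2) and the end-of-procedure sample. If the procedure is already over, the lower bound is 60 − 5 = 55 min.

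Against the healthy-subject data:
- Time of peak concentration was about 30–45 min (1.2.2.3). 55 − 45 = 10 and 55 − 30 = 25, so the bound lies about 10 to 25 min after the peak.
- At 16 mg, mean inhibition of at least 85% lasted about 6 h (1.2.2.3). 360 − 55 = 305 min, so about 5 h of that period could remain.
- At 8 mg, inhibition of at least 85% lasted 3 h on average (5.1.1). 180 − 55 = 125 min, so about 2 h could remain.

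**3. Range over assumed procedure end times**

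The documents give no time to procedure, so these end times are assumptions. Remaining time = duration of strong inhibition − procedure end.

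| Procedure ends | Left at 16 mg (about 6 h) | Left at 8 mg (about 3 h) |
|---|---|---|
| 1 h | 5 h | 2 h |
| 2 h | 4 h | 1 h |
| 4 h | 2 h | none |
| 6 h or later | none | none |

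**4. Rough residual concentration**

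Assume single-exponential decline from the peak: fraction = 2^(−(t − tmax)/t½), with tmax 0.5–0.75 h and t½ 1.3–9.2 h (1.2.2.3).
- At 55 min: from 2^(−0.417/1.3) = 0.80 to 2^(−0.167/9.2) = 0.99.
- At 8 h: from 2^(−7.5/1.3) = 0.02 to 2^(−7.25/9.2) = 0.58.
- At 48 h: at most 2^(−47.25/9.2) = 0.03.

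The half-life range comes from a study of 1 to 32 mg and is not attributed to 8 or 16 mg. None of these fractions is a threshold for the interaction.

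**5. Check of the protocol's 48 h statement**

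Section 9.1.4 says that 48 h includes at least five half-lives. At the longest reported value, 5 × 9.2 = 46 h, so the statement holds. It defines an adverse-event window, not an interaction limit.

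**6. Effect on the endpoints**

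The 15 and 30 min samples precede the 55 min bound. At the 60 min time point the PD sample is preferably drawn before the PK sample (7.2.3.2.1). The primary endpoint, its analysis and the 21 evaluable subjects per arm do not change.

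**The case against.** The strongest reply is that the protocol already deals with this. Section 1.4.2 binds sites as much as any other section (12.5 requires compliance with the whole approved protocol), 5.2.3 points to it, and 5.2.4 is an outright ban until the last PK sample. A reader might infer that the sections contradict each other. They do not: using a reversible agent throughout satisfies all of them. What stands is unequal strength and an end point unrelated to the reason for the rule.

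A second reply is that 55 min is an extreme. It needs the procedure to be finished within 55 min of injection and the 60 min sample to be taken at the edge of its window. That is right. The figure is a lower bound, and nothing in the documents shows that it would occur.

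A third reply concerns duration. A reader might infer from the open wording of 1.4.2, the two-day participation and the 48 h window in 9.1.4 that irreversible agents must be barred for 48 h. The documents do not go that far. Section 1.4.2 states no duration, 9.1.4 concerns adverse events, and the end-of-study visit is itself 48 h ±2 h. Section 5.1.1 treats 8 h as the longest acceptable time for interference with standard care when justifying the 16 mg dose. Section 1.4.2 also notes that clopidogrel and prasugrel worked as expected when given immediately after cangrelor was stopped. That is a different drug, but it ties the problem to occupancy and not to a fixed two days. Section 3.2 justifies the open-label design by the need to adapt antiplatelet treatment to the individual. A longer ban is therefore a clinical trade-off. This objection stands against a 48 h default, but not against a fixed time.

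**Conclusion.** The point holds as a minor inconsistency with a possible safety consequence. After an early procedure, 5.2.4 stops prohibiting clopidogrel and prasugrel while strong inhibition by ACT-246475 may still be present, and the sections a site is most likely to consult then contain only a request.

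The size of the harm cannot be given. It needs both an early procedure and a site that overlooks 1.4.2. The direct evidence for this drug is in vitro and limited to the prasugrel metabolite, and no section says when the interaction ends. The durations of inhibition come from healthy subjects and are approximate; carrying them over to acute MI is an assumption.

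**What to change.** 1. In 5.2.3 and the synopsis, replace the request with *must be used*, to match 1.4.2.
2. In 5.2.4 and the synopsis, take clopidogrel and prasugrel out of the list tied to the PK sample. Prohibit them from screening until a fixed number of hours after ACT-246475, at least 8 h, or until the last PK sample if that is later. Leave the other drugs as they are.
3. State the same end time in 1.4.2. The clinical team may choose up to 48 h post-dose. Count it from dosing and not from the end-of-study visit, which has a ±2 h window. Because 1.4.2 now has no end, a time shorter than 48 h could narrow it for some readers and should carry a short justification.

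The floor in step 2 ensures that no subject's present ban is shortened. It does not show that the interaction is over by then.

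The cost is a wording amendment to 1.4.2, 5.2.3, 5.2.4 and the synopsis, with the copy in SAP Appendix A brought into line. An investigator who wants clopidogrel or prasugrel right after an early procedure must use a reversible agent until the stated time. The same applies to resuming maintenance dosing, since exclusion criterion 3 bars only a loading dose. For those subjects this qualifies the statement in 8.4 that standard of care is unaffected. No new data are needed: 5.2.1 already covers therapy started up to 48 h, and 5.2.2 records the time of each oral P2Y12 dose. Sample size, blood draws and analysis stay the same.

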## 6 STUDY ENDPOINTS

### 6.1 Efficacy endpoints

Not applicable.

### 6.2 Pharmacokinetic and pharmacodynamic endpoints

#### 6.2.1 Pharmacodynamic endpoints

The primary PD endpoint is the response to the treatment defined for each subject as a PRU value < 100 at the 30 min post-dose time point, as measured via VerifyNow®. This corresponds to an IPA induced by ADP > 80% [Gaglia 2011, Gremmel 2009, Varenhorst 2009].

Additional PD endpoints related to the main ones will also be considered at each time point:

- PD profile over time based on absolute PRU values at 15, 30 and 60 min post-dose,
- PRU status (value < 100) at the 60 min post-dose time point.

#### 6.2.2 Pharmacokinetic endpoints

- Plasma concentrations of ACT-246475 will be determined at 15 min, 30 min, 1 h, and 8 h post-dose.
- Cmax.
- tmax.

### 6.3 Safety endpoints

The safety endpoints will be assessed up to end of study, i.e., over 48 h post treatment administration:

- Treatment-emergent AEs and SAEs.
- AE of specific interest (AESI): Hemorrhage.
- Change in vital signs (systolic and diastolic arterial blood pressure and pulse rate) from baseline to all assessed time points during the study.
- Change from baseline to for clinical laboratory tests.
- Treatment-emergent marked laboratory abnormalities.

## 7 VISIT SCHEDULE AND STUDY ASSESSMENTS

### 7.1 Study visits

The study is performed during a subject's hospital stay related to the qualifying AMI. This is considered to be a single visit, and assessments are listed in [Table 2](#).

#### 7.1.1 Screening/re-screening

Screening starts when the subject has provided informed consent. The date on which the first screening assessment is performed corresponds to the date of the study visit.

It is the responsibility of the investigator/delegate to obtain written informed consent from each subject participating in this study after adequate face-to-face explanation of the objectives, methods, and potential hazards of the study. The subjects who will be included in the study are considered as vulnerable and a specific consenting process is detailed in Section [1.4.3](#).

Subjects who have provided informed consent will be allocated a 7-digit subject identification number which will consist of: firsts 4 digits corresponding to the site identification number and lasts 3 digits corresponding to the sequential order of recruitment of the subjects from the site.

Subjects who have provided informed consent when the enrollment target has been met may still be randomized.

Re-screening is not permitted in this study.

#### 7.1.2 Unscheduled visits

Not applicable as the study is conducted over a single visit.

However, unscheduled assessments may be performed at any time during the study based on the judgment of the investigator and the results of these assessments will be recorded in the eCRF.

---

 A treatment-emergent AE is any AE temporally associated with the administration of study treatment (until 48 hours after study treatment administration) whether or not considered by the investigator as related to study treatment.

**Table 2 Visit and assessment schedule**

PERIOD	SCREENING	TREATMENT PERIOD					
Visit	Visit 1						
Time point	Pre-dose	0 min	15 min ±5 min	30 min ±5 min	60 min ±5 min	8 h / Post- procedure 	EOS 48 h ±2 h
Informed consent	X						
Eligibility	X						
Demographics and Medical history (including TIMI risk score and Killip class of MI)	X						
Physical examination	X						
Body weight and height (estimated)	X						
Previous/concomitant therapy	X		X				X
Vital signs (BP and PR)	X			X	X		X
PK blood sampling			X	X	X	X 	
VerifyNow®	X		X	X	X		
Laboratory tests	X						X
hsTnT	X						
s.c. injection of ACT-246475		X					
AEs/SAEs	X		X				X

(S)AE: (serious) adverse event; BP: blood pressure; EOS: End-of-Study; hsTnT: high sensitivity troponin T; MI: myocardial infarction; PCI: percutaneous coronary intervention; PK: pharmacokinetic; PR: pulse rate; s.c.: subcutaneous; TIMI: thrombolysis in myocardial infarction.

- The 8 h PK post-dose time point is flexible. If the subject gets an invasive procedure (PCI/angiography) within 8 h of study drug administration, the blood sample is to be collected at the end of the procedure. If no invasive procedure is performed within 8 h of study drug administration, the blood sample is to be collected approximately 8 h after study drug administration.

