## 3 OVERALL STUDY DESIGN AND PLAN

### 3.1 Study design

This is a prospective, multi-center, open-label, randomized, parallel-group, Phase 2, exploratory study of a single s.c. administration of ACT-246475, at two different dose levels, in subjects with AMI (STEMI or NSTEMI) scheduled for invasive strategy.

Approximately 42 adult subjects with confirmed diagnosis of AMI (STEMI or NSTEMI) and time from onset of symptoms of more than 30 min and less than 6 hours will be randomized to receive ACT-246475 either at the dose of 8 mg or 16 mg, in a 1:1 ratio injected s.c. into the thigh in addition to conventional standard-of-care treatment. Injection of ACT-246475 will be performed as soon as possible after randomization.

Subjects randomized who have not received ACT-246475 or who do not perform the 30-minute time point VerifyNow® assessment will be replaced.

The study will be conducted at approximately 3–8 sites in 2–3 countries (planned).

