### **7.2.3 Pharmacokinetic and pharmacodynamic assessments**

#### **7.2.3.1 Pharmacokinetic assessments**

##### *7.2.3.1.1 Procedures for blood sampling*

Blood will be collected by direct venipuncture or via an i.v. catheter placed in an antecubital vein in the arm in a 4 mL Monovette® or equivalent tubes containing ethylene diamine tetra-acetic acid (EDTA).

PK blood samples have to be processed within 30 min of collection. Instructions regarding sample collection, processing, labeling, and storage conditions are detailed in the laboratory manual.

The time points for PK assessment blood samples are described in [Table 2](#).

The date and exact actual clock time of collection of each blood sample will be entered in the eCRF.

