#### **10.3.4 Analysis of the pharmacokinetic variables**

Plasma concentrations per time point will be listed by dose group and subject, and summarized by time point and dose group using arithmetic and geometric mean, minimum, median, maximum, SD, SE, and two-sided 95% CI of the means and CV in %.

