6.9 Analysis of pharmacokinetic variables

The PK variables will be summarized and listed as provided using the PK set and will use the study treatment received.

The plasma PK parameters of ACT-246475 will be derived by non-compartmental analysis of the plasma concentration-time profiles. PK endpoints are: Maximum plasma concentration (C_{max}), and time to reach C_{max} (t_{max}).

Log-transformed value of C_{max} will be used in the analysis, while t_{max} will be used as is.

The PK parameters t_{max} , and $\log(C_{max})$ will be summarized by dose group using descriptive statistics, i.e., arithmetic mean, SD, geometric mean, minimum, median, maximum, standard error, and two-sided 95% CI of the means and coefficient of variation in %. Graphical representation of PK results over time will be provided using box-whisker plots.

Note that for t_{max} , the geometric mean and its 95% CI will not be calculated.

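### The last PK sample is labelled 8 h but may be drawn at the end of PCI or angiography, and the plan summarises both kinds of draw in one time-point row

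*Protocol*

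**What the plan says.** Protocol Table 2 schedules PK samples at 15, 30 and 60 min, each with a window of ±5 min, and then one further sample in a column headed with both 8 h and post-procedure. That column has no window. Its footnote explains: "The 8 h PK post-dose time point is flexible". If PCI or angiography is done within 8 h of dosing, "the blood sample is to be collected at the end of the procedure"; if not, "the blood sample is to be collected approximately 8 h after study drug administration".

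Protocol 3.1 describes the population as subjects "in subjects with AMI (STEMI or NSTEMI) scheduled for invasive strategy".

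The later sections drop the distinction:

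- Protocol 6.2.2: "Plasma concentrations of ACT-246475 will be determined at 15 min, 30 min, 1 h, and 8 h post-dose".
- Protocol 10.3.4: "Plasma concentrations per time point will be listed by dose group and subject, and summarized by time point and dose group", with arithmetic and geometric means, SD, SE, confidence intervals and CV.
- SAP 6.9 gives summary statistics for Cmax and tmax and adds: "Graphical representation of PK results over time will be provided using box-whisker plots". It has no post-procedure category and does not say whether PK displays use planned or actual times.
- SAP 10.1, on analysis periods and visit windows, sets no PK window. SAP 11, on changes and clarifications, does not mention the point.

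The information needed to separate the samples is collected. Protocol 7.2.3.1.1 states: "The date and exact actual clock time of collection of each blood sample will be entered in the eCRF". Procedures for the qualifying infarction are captured under Protocol 7.2.1 and SAP 5.4.5.

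**The concern.** One schedule column feeds one row of the concentration table and one box in the plot. That row would hold samples taken soon after dosing, when an early procedure ended, next to samples taken at about 8 h. Because an invasive strategy is planned for everyone, early draws are unlikely to be rare exceptions.

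Three things are at stake.

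- The row is the only PK information after 60 min, and its summary statistics would not refer to any particular time. Its CV would mix between-subject variability with variability in sampling time.
- A difference between the 8 mg and 16 mg groups in this row could partly reflect different procedure times. Protocol 5.1.3.1 describes no stratification, and with 21 subjects per arm a chance imbalance in timing is possible.
- The rationale for the high dose in Protocol 5.1.1 refers to platelet inhibition at 8 h, and Protocol 3.2 and 4.2 say the study is to support the choice of the Phase 3 dose. A concentration labelled 8 h is likely to be read in that context.

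**Working it through.** **Inputs**

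- Terminal half-life 1.3 to 9.2 h: Protocol 1.2.2.3, healthy men, s.c. doses of 1 to 32 mg.
- Peak concentration at about 30 to 45 min, and exposure essentially dose-proportional: same section.
- Time at which the procedure ends: not given in the documents, so varied here.
- Shape of decline: assumed log-linear from the time of the draw to 8 h. The documents do not state this.

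**The plan's own half-life figure.** Protocol 9.1.4 says that 48 h covers at least five half-lives. 5 × 9.2 h = 46 h, which is below 48 h, so the statement reproduces with the upper end of the range.

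**Size of the mixing.** For a draw at t hours, relative to a true 8 h draw:

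ratio = C(t) / C(8 h) = 2^((8 − t) / t½)

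| Draw at | t½ = 9.2 h | t½ = 1.3 h |
|---|---|---|
| 1 h | 2^(7/9.2) = 1.69 | 2^(7/1.3) = 41.8 |
| 2 h | 2^(6/9.2) = 1.57 | 2^(6/1.3) = 24.5 |
| 4 h | 2^(4/9.2) = 1.35 | 2^(4/1.3) = 8.4 |
| 6 h | 2^(2/9.2) = 1.16 | 2^(2/1.3) = 2.9 |
| 7 h | 2^(1/9.2) = 1.08 | 2^(1/1.3) = 1.7 |

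The footnote also allows the opposite case. A procedure that falls within the 8 h but ends at, say, 10 h gives a value lower than the 8 h value by a factor of 2^(2/t½), that is 1.16 to 2.9.

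**Effect on the row.** If a fraction q of a dose group is drawn at 2 h and the rest at 8 h, the row's geometric mean is 2^(6q / t½) times the true 8 h geometric mean. With q = 0.5 as an illustration, this is 2^(3/9.2) = 1.25 to 2^(3/1.3) = 4.95.

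**Effect on the dose comparison.** With dose-proportional exposure the expected 16 mg to 8 mg ratio is 2, which equals one half-life of elapsed time. At t½ = 1.3 h, a difference of 1.3 h between the arms in typical draw time would cancel or double the dose ratio. At t½ = 9.2 h the required difference would be 9.2 h, which is longer than the 8 h interval, so cancellation of that size would not arise from draws made within 8 h.

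**The case against.** The strongest reply is that the mixture is disclosed, recoverable and of little consequence. The Table 2 column names both kinds of sample, clock times and procedures are recorded, and concentrations are listed by subject, so the split can be made from data already collected. Onset of action, which Protocol 1.3 identifies as the question, is covered by the 15, 30 and 60 min samples. No hypothesis, test or decision rule uses the last sample. The list of outputs is a separate document (SAP 12) that is not available here, so the final display cannot be fully judged. All of this stands, and it limits the weight of the point. It does not supply a rule: followed as written, the plan yields one pooled row.

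Three stronger readings are tempting, and the documents do not support them.

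- A reader might infer that the row mixes concentrations differing by a fixed factor of about 1.6 to 24. That range belongs only to a procedure ending 2 h after dosing. Across procedures ending 1 to 7 h after dosing it runs from about 1.1 to about 42, and the half-lives come from healthy men rather than patients with infarction given 8 or 16 mg.
- A reader might infer that the PK objective exists to allow comparison with healthy subjects. Protocol 2.2 says only that PK is to be assessed in subjects with AMI.
- A reader might infer that Cmax and tmax will be derived from planned times. Neither document says so; the explicit planned-time rule in SAP 6.8.1.1 concerns PRU. Use of the scheduled time point for concentrations is an inference from Protocol 10.3.4, though it is the natural one given a single schedule column.

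**Conclusion.** The point holds for the late concentration row. The plan pools end-of-procedure and roughly 8 h samples under one label, and neither document says how to separate them, so the row's summary statistics and box would describe no single elapsed time.

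The size depends on procedure times that the documents do not give. It can be negligible if all draws fall near 8 h, which the footnote does not require, and large if procedures end early and the half-life is short. The tabulated factors rest on log-linear decline and on healthy-subject half-lives, and should be read as a conditional range.

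The consequence is confined to descriptive PK output. The primary endpoint (PRU at 30 min), its tests and the sample size are untouched. Cmax and tmax are largely unaffected if the peak falls at 30 to 45 min as in healthy subjects. They could be affected if uptake is much delayed in infarction, a possibility that Protocol 1.3 raises.

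**What to change.** Amend SAP 6.9 in three respects:

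- Summarise post-procedure samples and no-procedure samples (about 8 h) separately by dose group, or restrict the 8 h row to a pre-specified window of actual elapsed time. The window version also handles procedures that end after 8 h.
- Add a plot of concentration against actual elapsed time by dose group, marking post-procedure samples.
- State whether PK summaries and parameters use planned or actual times.

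This needs SAP wording and one extra figure, with no new data and no change to sampling. The cost is a smaller 8 h row. With an invasive strategy planned for all subjects it may contain few, so the number contributing should be shown with each summary. The documents offer no basis for a particular window width; the sponsor should choose and justify it before database lock.
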